1. BACKGROUND AND RATIONALE

1.1 Disease Background and Significance

Colorectal cancer remains the third most frequent cancer in both males and females, with approximately 142,000 cases reported in the United States in 2013². Approximately 50% of these patients will go on to develop metastatic disease, with the liver being the most frequent, and often only site of metastatic spread. Surgical resection is the only potentially curative therapy in these patients, however, recurrence following hepatectomy occurs in approximately 75% of cases^{3,4}. Due to the high frequency of recurrence, it has long been hypothesized that adjuvant systemic chemotherapy would have a role in this setting. In 2008 the results of a large, multi-center phase III randomized trial (EORTC Intergroup 40983) in which patients were randomized to FOLFOX4 administered perioperatively versus surgery alone were reported³. This study found that among resected eligible patients there was a 9.2% increase in progression-free survival in patients treated with perioperative FOLFOX ($p=0.025$), thus allowing the authors to conclude that perioperative chemotherapy has a benefit in these patients. However, a recent follow-up publication from this trial indicated that at a median follow-up of 8.5 years there was no statistically significant improvement in OS⁵. While it is felt by the oncology community that this trial was underpowered and therefore unable to demonstrate a significant improvement in OS (presumably when one indeed exists), nonetheless, it emphasizes the need for novel adjuvant trials in patients with resectable hepatic colorectal metastases⁶.

One such novel approach to the treatment of metastatic colorectal cancer is to use an immunotherapeutic strategy to stimulate the immune system's recognition and destruction of cancer cells. Multiple studies in primary colorectal cancer investigating the relationship between the tumor immune microenvironment and outcome have concluded that the immune cell type and density as well as the transcriptome, correlate with relapse-free and OS, and are equivalent if not superior in prognostic value to histopathologic staging⁷⁻⁹. More recently similar results have been found in studies focusing on patients undergoing surgery for hepatic colorectal metastases¹⁰⁻¹².

Therapeutic cancer vaccines represent a promising avenue in immunotherapy for multiple solid organ cancers. Considerable pre-clinical and clinical data has been generated using vector-based vaccines expressing tumor antigens, particularly Carcinoembryonic (CEA) and Mucin 1 (MUC1) antigens, indicating that these vaccines are safe and capable of eliciting anti-tumor immune responses¹³⁻¹⁶. In an effort to elicit additive or synergistic immune responses, a vaccine that expresses both CEA and MUC1, as well as several co-stimulatory molecules (PANVAC), was engineered into recombinant vaccinia (PANVAC-V) as a priming vaccination and fowlpox (PANVAC-F) as a multiple booster vaccination.

In a pilot study, PANVAC was evaluated in 25 patients with chemorefractory, metastatic gastrointestinal (esophageal, gastric, pancreatic, colorectal), breast, ovarian and lung cancers where it was found to be safe and demonstrated immune and clinical responses¹⁶. The safety and tolerability, as well as further evidence of clinical benefit of this vaccine approach, were reported in a second pilot study of 26 patients with chemorefractory metastatic breast and ovarian cancer¹⁷. In an effort to evaluate PANVAC in a more limited disease setting, PANVAC was studied in a multicenter trial of patients with resected hepatic colorectal metastases. The purpose

of this trial was to compare two methods of PANVAC vaccination for efficacy using recurrence-free (RFS) and OS as endpoints. The two methods were prime-boost immunization with dendritic cells modified ex-vivo with PANVAC versus PANVAC administered subcutaneously¹. Patients with liver and lung metastases (the majority had liver) that had undergone complete resection and had received at minimum 2 months of perioperative chemotherapy were eligible. Patients in the dendritic cell/PANVAC-V arm (DC/PANVAC-V) received one dose followed by three doses of the DC/PANVAC-F at monthly intervals. The second arm received a onetime PANVAC-V priming dose followed by 3 doses of PANVAC-F at monthly intervals. Both arms received doses of GM-CSF subcutaneously for four days at the injection sites after each vaccination. Two-year (RFS and OS were the clinical endpoints measured. Interestingly, there was not a statistically significant difference in RFS or OS when comparing the two arms of the study. However, when the two vaccination arms were combined and compared to a contemporary control cohort of unvaccinated patients there was a significant difference in OS in favor of the vaccinated patients, with the median OS of the contemporary cohort at 44.1 months while that of the vaccinated group had not been reached. Importantly, the RFS between the two groups was not significantly different, indicating the importance of further trials to better characterize the effect of PANVAC in this patient population, with the use of OS as the preferred clinical endpoint. While this difference in survival was remarkable, the trial has been criticized because the control group and the vaccinated groups were not randomized. Thus, in order for PANVAC to move forward into phase III testing, this result will need to be validated with a randomized control group treated with standard of care multimodality therapy.

[figure not shown]

Figure 1. A) Recurrence-free survival for vaccinated patients combined versus contemporary, unvaccinated controls. RFS was measured from the date of metastasectomy until documented disease recurrence at any site. Median RFS (95% CI) was 21.9 (16.9-38.8) and 25.7 (20.0-37.2), months, respectively. B) OS for vaccinated patients combined compared with contemporary, unvaccinated controls. OS was measured from metastasectomy until death from any cause. Patients were censored on the date of last known follow-up. Median OS (95% CI) was not reached and 44.2 (36.2-63.4), months, respectively¹. *95% CI indicates 95% confidence interval

Further clinical evidence in support of the use of PANVAC in gastrointestinal cancers comes from our group. In a first-in-man Phase I study, patients with adenocarcinoma of the pancreas were treated using a combination of EUS-guided intrapancreatic tumor injection and systemic boost using PANVAC-F and PANVAC-V. The study represents the translation of our unique

demonstration in murine models of bladder¹⁸ and orthotopic mammary tumors¹⁹ that tumor anergy to systemic immunization could be overcome by immunization into the tumor microenvironment using antigen-encoding vaccinia recombinants. Consented patients with locally advanced or minimally metastatic pancreatic cancer received EUS-guided intrapancreatic injections (IT) of recombinant PANVAC-F (Fowlpox encoding MUC-1, CEA, TRICOM), systemic subcutaneous (SC) PANVAC-V (vaccinia) and SC PANVAC-F boosts. Systemic SC vaccines were accompanied by subcutaneous rH-GM-CSF, 100 mcg X 4 days. Patients received 2 intrapancreatic injections of PANVAC-F (2 weeks apart) with systemic PANVAC-V and PANVAC-F boosts given with GM-CSF extending to day 71 (total of 2 IT PANVAC-F, 1 SC PANVAC-V, 4 SC PANVAC-F). Patients were allowed to transition to standard care at day 31. Patients were evaluated for toxicity and tumor progression. In this dose escalation study, the first cohort of 6 patients received IT PANVAC-F (108 PFU), SC PANVAC-V (2 X 108), and SC PANVAC-F (109). The second dose cohort of 8 pts received IT PANVAC-F (109 PFU), SC PANVAC-V (2 X 108), and SC PANVAC-F (109). At dose level 1, two of six patients were removed from study after approximately two weeks due to rapid disease progression and died one and six months after trial initiation respectively. At dose level 2, one patient was removed due to rapidly progressive disease and died at 1 month, and a second patient withdrew following 1 IT inoculation and died at month 16. Of the remaining 10 pts, 3 presented with distant metastatic disease (median survival 7 mos, range 1-25) and 7 presented without distant metastases (median survival 16 mos, range 3-35). Of note, none of the 7 patients presenting without metastatic disease developed distant visceral metastases by imaging available to us but died of sequelae associated with progressive localized disease. Of the above 10 pts, all but one transitioned initially to treatment with gemcitabine-based therapy (the remaining patient did not begin systemic treatment). Initial RNAseq transcriptome analysis comparing Day 1 and Day 14 fine needle aspirate (FNA) samples demonstrated a significant increase in a series of chemokines associated with the induction of an immune response in the tumor microenvironment. A planned series of immunologic and genetic analyses are underway. The results demonstrate that the “first in man” intra-pancreatic administration of recombinant poxvirus was well tolerated with the complete regimen suggesting an encouraging period of stable disease. The finding that none of the patients who presented without distant visceral metastases developed such, is thought to be due to the generation of a systemic immune response with effects on seeded metastatic cells. Analysis of local and systemic immune responses is currently proceeding and we hope will provide further insights.

Nevertheless, it is important to consider that, when dealing with immunotherapy, the tumor microenvironment determines whether a patient can make an effective immune response to his/her tumor. Tumor cells can induce an immunosuppressive milieu through multiple tolerogenic factors and expression of inhibitory surface receptors that create a shield around the tumor, resulting in evasion of the immune response. Two such mechanisms include (a) expression of PD-L1 in tumor or infiltrating cells, which triggers PD-1 on T-cells, inhibiting T-cell activation and expansion of previously activated T-cells; and (b) recruitment of T-regulatory cells, which are thought to suppress antitumor immune responses, into the tumor.

Although clinical evidence may support the use of CV301 (next generation PANVAC), pre-clinical data have shown that a similar antigen expressing poxvirus vaccine is able to up-regulate levels of PD-L1 in the tumor microenvironment, thus preventing the immune system from killing

cancer cells. This suggests that a combination of CV301 with anti-PD-1 therapy might be a more efficacious addition to cytotoxic chemotherapy than either CV301 or a checkpoint inhibitor alone.

The antibody-drug known as Nivolumab, binds to PD-1 with high affinity inhibiting the binding of PD-1 to its ligands PD-L1 and PD-L2. In the clinic, Nivolumab has been investigated both as monotherapy and in combination with chemotherapy, targeted therapies, and other immunotherapies for the treatment of several types of cancer. Most studies are still ongoing and, as such, the safety profile of Nivolumab combinations continues to evolve. Nevertheless, in association with chemotherapy (platinum-based) the safety profile of Nivolumab appeared manageable and consistent with that reported for the monotherapy regimen, with no safety concerns identified²⁰. Furthermore, in the currently ongoing trial CV301-2015-201 (NCT02840994), three patients have been exposed to administrations CV301 (MVA/FPV) plus several doses of Nivolumab (13, 8 and 2 doses respectively). No SAEs, adverse events of special interest or dose-limiting toxicities have been observed to date (as of 09-Apr-2018). Also, no immune-mediated adverse events of special interest have been reported from this cohort. In this study, we aim to determine if perioperative vaccination with CV301 in combination with Nivolumab and perioperative systemic chemotherapy improves OS as compared to Nivolumab plus perioperative chemotherapy in patients undergoing surgical resection of hepatic-limited metastatic colorectal cancer.

1.2 Clinical Profile of MVA-BN and Recombinant MVA-based Vaccines

MVA-BN Vector Backbone

CV301 is a next-generation product based on the same antigen inserts as PANVAC, but using the non-replicating MVA-BN vector as priming component instead of PANVAC's replicating vaccinia vector.

To date, 22 clinical trials evaluating the safety and immunogenicity of MVA-BN have been completed and one clinical trial is ongoing. Currently, more than 8,800 subjects have been exposed to MVA-BN including risk groups with contraindications to conventional smallpox vaccines. Furthermore, BN has evaluated the safety and immunogenicity of MVA-BN-based recombinant vaccines (including MVA-BN-Filo) in healthy subjects, HIV infected individuals, populations with cancer and children. In total, for MVA-BN and MVA-BN-based recombinant vaccines, the exposure sums up to more than 13,300 subjects.

Furthermore, BN has evaluated the safety and immunogenicity of MVA-BN-based recombinant vaccines in more than 900 subjects including healthy subjects, HIV infected individuals and populations with cancer and children in completed trials. In recombinant MVA vaccine trials, doses up to at least 5×10^8 TCID₅₀ (nominal titer) were administered applying varying schedules of repeat vaccinations, e.g. a 3-dose schedule was used for recombinant HIV vaccines and multiple vaccinations have also been performed in subjects receiving a recombinant therapeutic breast cancer vaccine (MVA-BN-HER2).

Furthermore, more than 3,600 subjects have been enrolled in completed and ongoing clinical trials with MVA-BN Filo®, ranging from Phase 1 to Phase 3 trials. The preliminary safety data are consistent with the previous experience.

In total, for MVA-BN and MVA-BN-based recombinant vaccines, the exposure sums up to more than 13,300 subjects (more than 8,800 with MVA-BN, more than 900 with recombinant vaccines other than MVA-BN Filo, and more than 3,600 with MVA-BN-Filo). For more details, refer to the current IB of MVA-BN-CV301 vaccine.

1.3 Safety Overview for the Combination CV301 plus Anti-PD-1 Therapy Clinical Trial CV301-2015-201

The safety and tolerability of CV301 in combination with Anti-PD1-Therapy is currently evaluated in the ongoing trial CV301-2015-201 (A Phase 1/2 Trial of CV301 in Combination with Anti-PD-1 Therapy versus Anti-PD-1 Therapy alone in Subjects with Non-Small Cell Lung Cancer, ClinicalTrials.gov Identifier: NCT02840994).

In the Phase 1 part of this trial, 12 subjects with various CEA/MUC-1 positive cancers have been enrolled, 6 male and 6 female subjects, aged between 39 and 77 years (Gatti-Mays 2019) (GATTI-MAYS, M. E., STRAUSS, J., DONAHUE, R. N., PALENA, C., DEL RIVERO, J., REDMAN, J. M., MADAN, R. A., MARTE, J. L., CORDES, L. M., LAMPING, E., ORPIA, A., BURMEISTER, A., WAGNER, E., PICO NAVARRO, C., HEERY, C. R., SCHLOM, J. & GULLEY, J. L. 2019. A Phase 1 Dose Escalation Trial of BN-CV301, a Recombinant Poxviral Vaccine Targeting MUC1 and CEA with Costimulatory Molecules. *Clin Cancer Res*).

In the ongoing Phase 1b part of the trial, 12 subjects (nine females and three males between 48 and 74 years) were enrolled: four subjects in cohort 1 received up to 15 doses of combination of CV301 and nivolumab over a period of up to approximately 16 months. In cohort 2, eight subjects received up to nine doses combination of CV301 and pembrolizumab over a period of up to nine months.

1.3.2 Clinical Trial CV301-BLD-001

This is an ongoing, BN-sponsored Phase 2, multicenter, single-arm trial of CV301 in combination with PD-1/L1 blockade in patients with locally advanced or metastatic urothelial bladder cancer (ClinicalTrials.gov Identifier: NCT02840994).

As of June 30th, 2019, 37 patients were dosed with CV301 in combination with atezolizumab. Data is still preliminary.

1.3.3 Clinical Trial 2017-1189 / BN-IST-017

This is an ongoing, Investigator-sponsored Phase 1/2, multicenter, open label, randomized, one-arm trial of CV301 with PD-1/L1 blockade in patients with hepatic-limited metastatic colorectal cancer or pancreatic adenocarcinoma (ClinicalTrials.gov Identifier: NCT03628716).

As of June 30th, 2019, six patients were enrolled and dosed with CV301 in combination with durvalumab. Data is still preliminary.

The overall frequency of immune mediated events under combination treatment of CV301 plus anti-PD1 seems to be in line with previously published experience for anti-PD1 alone ([Brahmer, 2018](#)) (Brahmer JR, Lacchetti C, Schneider BJ, Atkins MB, Brassil KJ, Caterino JM, Chau I, Ernstoff MS, Gardner JM, Ginex P, Hallmeyer S, Holter Chakrabarty J, Leighl NB, Mammen JS, McDermott DF, Naing A, Nastoupil LJ, Phillips T, Porter LD, Puzanov I, Reichner CA, Santomasso BD, Seigel C, Spira A, Suarez-Almazor ME, Wang Y, Weber JS, Wolchok JD, Thompson JA. (2018).Management of Immune-Related Adverse Events in Patients Treated With Immune Checkpoint Inhibitor Therapy: American Society of Clinical Oncology Clinical Practice Guideline. J Clin Oncol. 2018; 36:1714-1768).

2. STUDY OBJECTIVES

2.1 Primary Objective

Determine if perioperative vaccination with CV301 in combination with nivolumab, systemic chemotherapy and surgical resection improves 3 year OS as compared to perioperative nivolumab, systemic chemotherapy and surgical resection in patients with hepatic-limited metastatic colorectal cancer. Overall survival is defined as time from metastasectomy to date of death from any cause.

2.2 Secondary Objectives

- Compare 3- year recurrence-free survival (RFS) between the experimental and control treatment groups.
- Compare 3-year OS between the experimental and control groups
- Compare OS (in both the experimental and control groups) to historical controls
- Evaluate the best overall response rates (both by RECIST 1.1 and surgical pathology) between the experimental and control groups.

- Compare the pathologic complete response rate to neoadjuvant therapy in resected tumor tissue between the experimental and control groups.
- In patients who experience a recurrence after surgery, evaluate the proportion of patients amenable to complete re-resection/ablation between the experimental and control treatment groups.
- In patients who experience a recurrence after protocol therapy, compare the progression free survival post-recurrence between the experimental and control groups.
- Evaluate the perioperative surgical outcomes (complications and severity scores) between the experimental and control groups.
- Compare 3-year OS from the date of registration between experimental and control groups

2.3 Correlative/Exploratory Objectives

Analyze the following laboratory experiments for biomarker analyses and correlate with response to therapy and clinical outcomes:

- mRNA signature in tumor tissue pre- and post-therapy by whole transcriptome sequencing using RNAseq
- Genomic profiling of metastatic and primary tumor DNA
- CEA and MUC-1 antigen-specific immune response in pre- and post-therapy peripheral blood by intracellular cytokine staining and/or ELISPOT or other validated assays.
- Other tumor-associated antigen-specific immune response measures may be assessed if adequate samples are available
- TCR clonality assays
- Serum cytokine, and serum soluble factors
- PD-1/PD-L1 staining in pre- and post-therapy tumor tissue.
- Immunoscore by IHC

3 ELIGIBILITY CRITERIA

3.1 Inclusion Criteria

Subjects must meet all of the following applicable inclusion criteria to participate in this study:

1. Written informed consent and HIPAA authorization for release of personal health information prior to registration. **NOTE:** HIPAA authorization may be included in the informed consent or obtained separately.
2. Age \geq 18 years at the time of consent.
3. ECOG Performance Status of \leq 2 and/or sufficient to undergo both perioperative systemic chemotherapy and hepatic surgery as determined by surgical and medical oncology evaluations.
4. Histologically confirmed hepatic-limited metastatic colorectal cancer.

5. Genomic testing results are required. FoundationOne platform is preferred, however results from an equivalent genomic platform may be used after discussion with the sponsor investigator.
6. Completely resectable disease as determined by the guidelines below and surgical oncology evaluation. Patients with bilobar disease that requires resection and ablation are allowed provided the surgical oncologist can render the patient NED (no evidence of disease) at the conclusion of the operation. Synchronous primary colorectal and metastatic hepatic tumors are eligible, provided all disease can be resected in a single operation. **NOTE:** Subjects who had surgery for their primary tumor prior to registration to this trial are still eligible.
Additionally:
 - No radiographic evidence of involvement of: extrahepatic bile ducts, main portal vein or celiac/retroperitoneal lymph nodes.
 - Adequate predicted functional liver remnant (FLR) as deemed by the individual site surgical oncologist.
7. Patients must be treatment naïve with respect to their stage IV colorectal cancer. History of prior adjuvant systemic chemotherapy containing oxaliplatin is allowed as long as it has been greater than 12 months from completion of oxaliplatin to study enrollment. **NOTE:** Neoadjuvant pelvic chemoradiotherapy as part of the management of synchronous metastatic rectal cancer is allowed, provided chemoradiation was completed prior to enrollment on study.
8. Demonstrate adequate organ function as defined in the table below. All screening labs must be obtained within 28 days prior to registration.

System	Laboratory Value
Hematological	
Platelet Count	$\geq 100,000 \text{ mm}^3$
Absolute Neutrophil Count (ANC)	$\geq 1500 \mu\text{L}$
Hemoglobin (Hgb)	$\geq 9 \text{ g/dL}$
Renal	
Creatinine OR Calculated Creatinine Clearance ¹	< 1.5x ULN OR $\geq 60 \text{ mL/min}$ for participants with creatinine levels $> 1.5x \text{ ULN}$
Hepatic	
Total Bilirubin	$\leq 1.5 \times \text{ upper limit of normal (ULN)}^2$
Aspartate aminotransferase (AST)	$\leq 5 \times \text{ ULN}$; given presence of liver metastases
Alanine aminotransferase (ALT)	$\leq 5 \times \text{ ULN}$; given presence of liver metastases
Alkaline Phosphatase	$< 2.5 \times \text{ ULN}$
Coagulation	
International Normalized Ratio (INR) or prothrombin time (PT) or activated partial thromboplastin time (aPTT)	$\leq 1.5 \times \text{ ULN}$ unless participant is receiving anticoagulant therapy, in which case they must be on a stable dose

¹Cockcroft-Gault formula will be used to calculate creatinine clearance

²If patient has conditions of congenital hyperbilirubinemia, then patient must have isolated hyperbilirubinemia (e.g. no other liver function test abnormalities) with maximum bilirubin $< 2 \times$ institutional ULN

9. Females of childbearing potential must have a negative serum pregnancy test within 24 hours of study drug. **NOTE:** Females are considered of childbearing potential unless they are surgically sterile (have undergone a hysterectomy, bilateral tubal ligation, or bilateral oophorectomy) or they are naturally postmenopausal for at least 12 consecutive months without another cause, or a documented serum follicle stimulating hormone (FSH) ≥ 35 mIU/mL. Should a woman become pregnant or suspect she is pregnant while participating in this study, she should inform her treating physician immediately.
10. Females of childbearing potential and male participants must be willing to abstain from heterosexual intercourse or to use contraception as outlined in Section 5.6.
11. As determined by the enrolling physician or protocol designee, ability of the subject to understand and comply with study procedures for the entire length of the study.

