12. Participants with history of life-threatening toxicity related to prior immune therapy (e.g. anti-CTLA-4 or anti-PD-1/PD-L1 treatment or any other antibody or drug specifically targeting T-cell co-stimulation or immune checkpoint pathways) except those that are unlikely to re-occur with standard countermeasures (e.g. Hormone replacement after adrenal crisis)
13. Patients with serious or uncontrolled medical disorders.
14. Treatment with botanical preparations (e.g. herbal supplements or traditional Chinese medicines) intended for general health support or to treat the disease under study within 2 weeks prior to randomization/treatment.
15. History of allergy or hypersensitivity to study drug components.
16. Has received a live vaccine within 30 days of the planned start of study therapy. **NOTE:** seasonal flu vaccines for injection are generally inactivated vaccines and are allowed, however intranasal influenza vaccines are live attenuated vaccines and are not allowed.
17. History of allogenic stem cell or solid organ transplant.

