6. TOXICITIES AND DOSE DELAYS/DOSE MODIFICATIONS

Guidelines for dose delays and dose modifications are described below, and applicable to the start of each cycle as well as during the cycle if treatment-related toxicities occur. Subjects enrolled in this study will be evaluated clinically and with standard laboratory tests before and at regular intervals during their participation in this study as specified in Study Calendar & Evaluations. The NCI Common Terminology Criteria for Adverse Events (CTCAE) v4 will be used to grade adverse events. Subjects will be evaluated for adverse events (all grades), serious adverse events, and adverse events requiring study drug interruption or discontinuation as specified in Study Calendar & Evaluations.

Dose modifications are always based on the dose used in the previous cycle.

The investigator may attribute each toxicity event to the vaccine, nivolumab, mFOLFOX6, or any component of the combination therapy. Reduction or holding of one agent and not the other agent is appropriate if, in the opinion of the investigator, the toxicity is related to one of the study drugs. For example, if mFOLFOX6 is held due to an AE attributed to that component or the combination, then the vaccine and/or Nivolumab may continue to be administered. The drug to which the investigator is attributing the AE must be documented. If there is more than a 2-day delay for any reason, administration of study drugs should be re-aligned so that the chemotherapy falls within +2 days with the next cycle.

6.1 mFOLFOX6

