Contraindicated in: Hypersensitivity to oxaliplatin, severe renal impairment ($\text{CrCl} < 30 \text{ mL/min}$), pregnant/breastfeeding, peripheral neuropathy with severe functional impairment prior to the first cycle. Use caution in patients with: Previous pelvic radiotherapy, recent myocardial infarction, uncontrolled angina, uncontrolled hypertension, uncontrolled cardiac arrhythmias, uncontrolled congestive heart failure, baseline > 3 loose bowel movements per day (in patients without colostomy or ileostomy), symptomatic peripheral neuropathy. Toxicities include: myelosuppression \pm infection, neuropathy, nausea, vomiting, diarrhea, transaminitis, fatigue, mucositis, abdominal pain, bleeding, rash, hand-foot syndrome, pharyngolaryngeal dysesthesia, arterial or venous thromboembolism, venous occlusive disease, hypersensitivity reaction, cardiotoxicity, hemolytic uremic syndrome, nephrotoxicity, pancreatitis, pneumonitis, rhabdomyolysis, RPLS.

The following dose reductions should be used for all toxicities:

Agent	Dose Level 0	Dose Level -1	Dose Level -2	Dose Level -3
Oxaliplatin	85 mg/m ²	65 mg/m ²	50 mg/m ²	Discontinue
Leucovorin	400 mg/m ²	400 mg/m ²	400 mg/m ²	Discontinue
Fluorouracil bolus	400 mg/m ²	320 mg/m ²	260 mg/m ²	Discontinue
Fluorouracil	2400 mg/m ²	1900 mg/m ²	1500 mg/m ²	Discontinue

*Leucovorin is delayed or omitted if bolus fluorouracil is delayed or omitted

*Institutional standards for measuring height and weight during chemotherapy administration should be used and dose adjusted according to institutional standards.

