6.1.1 Renal Impairment

mFOLFOX6 is contraindicated in severe renal impairment ($\text{CrCl} < 30 \text{ mL/min}$).

CrCl (mL/min)	Oxaliplatin	Leucovorin	Fluorouracil
50-80	No change	No change	No change
30-49	No change, monitor	No change	No change, monitor
<30	Discontinue	No change	Consider dose reduction to next lower dose level

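### The renal entry criterion sets no clearance floor when creatinine is below 1.5x ULN, so some older, low-weight patients can meet it with a clearance at which the protocol contraindicates mFOLFOX6

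*Combined protocol and SAP*

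**What the plan says.** Section 3.1, item 8, defines adequate organ function. Its renal row, "Creatinine OR Calculated Creatinine Clearance", has two branches. The first is creatinine below 1.5x ULN, with no condition on clearance. The second is a calculated clearance of at least 60 mL/min, but only "for participants with creatinine levels" above 1.5x ULN. A footnote names Cockcroft-Gault as the formula. Nothing else in 3.1 or 3.2 sets a clearance floor, an upper age limit or a weight limit.

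Section 6.1 lists, for mFOLFOX6, "Contraindicated in: Hypersensitivity to oxaliplatin, severe renal impairment", defined as clearance below 30 mL/min. Section 6.1.1 repeats it: "mFOLFOX6 is contraindicated in severe renal impairment". In the 6.1.1 table the below-30 band stops oxaliplatin, leaves leucovorin unchanged and, for fluorouracil, says "Consider dose reduction to next lower dose level". Both arms receive mFOLFOX6 before and after surgery (5.1.2 and 5.1.4).

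**The concern.** The entry criterion and the treatment section measure renal function on different scales. Serum creatinine takes no account of age, sex or weight, and Cockcroft-Gault clearance depends on all three. A patient can therefore satisfy item 8 on creatinine and still be in the clearance band where the backbone of both arms is contraindicated.

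Three things would follow for such a patient:

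- Randomisation comes before any protocol therapy (section 4), so the problem could surface only after allocation, in a patient who cannot receive the assigned oxaliplatin regimen.
- In Arm B, nivolumab and MVA-BN-CV301 are given on Days -28 and -14, before the first mFOLFOX6 dose (5.1.2). Late discovery would then follow two investigational doses. This requires that nobody calculated clearance from the chemistry drawn at screening and on those two days.
- If completely resected, the patient still counts as evaluable for efficacy under 12.6, which asks only for one dose of protocol therapy and complete resection.

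Actual oxaliplatin exposure at this clearance would need a site to act against 6.1.

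**Working it through.** There is no figure in the plan to reproduce. The check is whether patients who satisfy the creatinine branch can have a clearance below 30 mL/min.

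**Inputs**

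- Entry limit: creatinine below 1.5x ULN (3.1, item 8). The main check uses 1.4x ULN, inside the limit.
- Contraindication: clearance below 30 mL/min (6.1 and 6.1.1).
- Formula: Cockcroft-Gault, CrCl = (140 − age) × weight × s / (72 × creatinine), with s = 0.85 for women and 1 for men.
- Creatinine ULN: not given in the documents. Assumed to be 0.9 to 1.3 mg/dL.
- Ages and weights: illustrations. The documents give no distribution of age, weight or creatinine.

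**Worked case.** Woman, 80 years, 45 kg: 60 × 45 × 0.85 = 2295.

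- ULN 0.9: creatinine 1.4 × 0.9 = 1.26; 2295 / (72 × 1.26) = 25.3 mL/min.
- ULN 1.3: creatinine 1.4 × 1.3 = 1.82; 2295 / (72 × 1.82) = 17.5 mL/min.

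**Clearance (mL/min) at 1.4x ULN, by assumed ULN (mg/dL)**

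| Profile | 0.9 | 1.0 | 1.1 | 1.2 | 1.3 |
|---|---|---|---|---|---|
| Woman, 80 y, 45 kg | 25.3 | 22.8 | 20.7 | 19.0 | 17.5 |
| Woman, 75 y, 50 kg | 30.5 | 27.4 | 24.9 | 22.8 | 21.1 |
| Woman, 70 y, 50 kg | 32.8 | 29.5 | 26.8 | 24.6 | 22.7 |
| Man, 80 y, 55 kg | 36.4 | 32.7 | 29.8 | 27.3 | 25.2 |
| Man, 60 y, 70 kg | 61.7 | 55.6 | 50.5 | 46.3 | 42.7 |
| Number below 30 | 1 | 3 | 4 | 4 | 4 |

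**Break-even ULN.** A profile falls below 30 at 1.4x ULN once the ULN exceeds (140 − age) × weight × s / (72 × 30 × 1.4), where the denominator is 3024. In table order: 2295/3024 = 0.76; 2762.5/3024 = 0.91; 2975/3024 = 0.98; 3300/3024 = 1.09; 5600/3024 = 1.85 mg/dL.

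**How high creatinine must be.** The 80-year-old, 45-kg woman reaches 30 mL/min at 2295 / (72 × 30) = 1.06 mg/dL. That is 1.18x ULN if the ULN is 0.9 and 0.97x if it is 1.1, so from a ULN of 1.1 upward it lies within the normal range.

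**At the edge of the limit (1.49x ULN).** With a ULN of 0.9 to 1.2, a 50-kg woman has 26.4 down to 19.8 mL/min at age 80 and 28.6 down to 21.5 at age 75, below 30 at every value. A 70-kg, 70-year-old stays above 30: 43.1 down to 32.4 for a woman over the same ULN range, and 41.5 down to 32.6 for a man with a ULN of 1.1 to 1.4.

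**Ordering.** A 50-year-old, 65-kg man at 1.6x ULN has 90 × 65 / (72 × 1.6 × ULN), which is 56.4 (ULN 0.9) down to 39.1 (ULN 1.3). All are below 60, so the row rejects him. It accepts the 80-year-old woman at 1.4x ULN. Her highest value (25.3) is below his lowest (39.1), so different ULNs for the two sexes, within this range, do not change the comparison.

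**The case against.** The strongest reply is that one row is being read in isolation. Item 3 requires ECOG 2 or better "and/or sufficient to undergo both perioperative systemic chemotherapy and hepatic surgery as determined by surgical and medical oncology evaluations", and an oncologist could hardly certify fitness for a regimen that the protocol contraindicates. Exclusion 13 covers "Patients with serious or uncontrolled medical disorders". Multidisciplinary discussion and surgical evaluation are required as well. At dosing, the section 6 rules are "applicable to the start of each cycle as well as during the cycle if treatment-related toxicities occur", and the 6.1.1 table cannot be used without a clearance value. Creatinine is measured repeatedly before and during chemotherapy.

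The profiles are also chosen near the cut-off: four of the five are aged 70 or more and weigh 55 kg or less. A ULN of 1.3 is high for a woman, so 17.5 mL/min is the extreme of the range. Almost any serum-creatinine criterion can be made to rank two chosen patients the wrong way round.

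Most of this stands, and it limits the weight of the point. Few such patients are likely to be judged fit for hepatectomy, and their full eligibility is not claimed here. But the entry safeguards rest on judgement and carry no renal threshold. The connective in item 3 lets ECOG alone satisfy it, the multidisciplinary discussion concerns resectability, and the section 6 rules act only after randomisation. The study calendar lists creatinine but not calculated clearance. Dropping the extreme ULN does not change the finding: the 80-year-old, 45-kg woman is below 30 even at 0.9.

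**Conclusion.** The concern holds as a gap between 3.1 and 6.1. The renal row admits some patients whose Cockcroft-Gault clearance is below the level at which the protocol contraindicates the backbone regimen, and no other entry criterion sets a clearance limit.

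The size depends on the assumed ULN. Of the five profiles at 1.4x ULN, one is below 30 at a ULN of 0.9, three at 1.0, and four at 1.1 to 1.3. The gap is confined to older, lighter patients, and no frequency can be stated from the documents. The consequence is an avoidable randomisation and, in Arm B, possibly two avoidable investigational doses. Confidence in the wording gap is high. The practical effect is probably small, and no sample size, alpha or power figure changes. It is a point to consider, not a flaw in the primary analysis.

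**What to change.** Amend the renal row so that Cockcroft-Gault clearance is calculated for every patient at screening, and require at least 30 mL/min whatever the serum creatinine. The existing 60 mL/min requirement above 1.5x ULN can stay.

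The cost is one wording amendment. Creatinine and weight are already collected at screening (section 7), so no new test is needed. A few frail patients would be screened out, all of whom 6.1 already bars from mFOLFOX6. Some of them might have received fluorouracil and leucovorin under the 6.1.1 table, but that is not the assigned regimen.
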